	
 
1. To determine the overall response rate at day 28 of treatment
 
2. To calculate the duration of response
 
3. To calculate the incidence of serious infections (overall, viral, bacterial, fungal, parasitic) by day 90 of treatment
 
4. To determine the cumulative steroid exposure through days 28 and 90 of treatment
 
5. To determine the cumulative incidence of 1-year NRM, relapse, chronic GVHD and overall survival
 
6. To determine the cumulative incidence of steroid-refractory GVHD in patients by day 90 of treatment
 
 
Exploratory Objectives:
 
 
1. To measure quality of life (physical functioning and neuropsychiatric well-being) through day 180
 
2. To calculate growth velocity in study patients over one year
 
3. To calculate the MAGIC algorithm probability at day 28 of treatment
 

Number of Subjects	50
Inclusion Criteria	
 
1. Newly diagnosed GVHD that meets criteria for Minnesota standard risk (see section 9.0) except isolated skin rash <25% body surface area without other manifestations
 
2. Ann Arbor 1 GVHD by biomarkers
 
3. GVHD not previously treated systemically (topical therapies and non-absorbed steroids are allowed)
 
4. Any donor type, HLA-match, conditioning regimen is acceptable
 
5. Age 0-21 years at the time of screening
 
6. Signed and dated written informed consent obtained from patient or legal representative and assent from pediatric patients capable of providing assent
 

Exclusion Criteria	
 
1. Patients treated for GVHD with >0.5 mg/kg/day prednisone or any steroid treatment for GVHD for more than 2 days prior to screening*
 
2. Patients receiving corticosteroids >0.1 mg/kg prednisone (or other steroid equivalent) for any indication within 7 days before the onset of acute GVHD except for adrenal insufficiency,
 

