#### **4.7 Exploratory Endpoints**

1. GVHD biomarker concentrations (ST2 and REG3) and their associations with clinical endpoints at day 28
2. Patient reported outcomes (QOL) through day 180
3. Linear growth velocity (change in height, relative to sex- and age-means)

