### **7.7 Duration of Follow-Up**

Patients will be followed until 1 year post-enrollment, withdrawal of consent or until death, whichever occurs first. HCT patients are followed closely and frequent clinical evaluations are the norm. While the following outlines the minimum frequency of follow-up evaluations, it is anticipated that the majority of patients will be evaluated more frequently.

During the first 4 weeks of participation, patients will be seen at least weekly for assessment of their GVHD. Patients will also be evaluated at days 42, 56, 90, 180 and 365. Additionally, patients will be evaluated if GVHD flares.

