## **7.9 Patient Replacement**

Patients who enroll in the study but (1) do not receive prednisone treatment or (2) initiate prednisone at a dose higher than 0.5 mg/kg (rounding to achieve a feasible dose is allowed) will be replaced. The number of patients and reason(s) for replacement will be reported and will be used to assess the feasibility of the study design. Patients who withdraw consent or are lost to follow-up prior to day 28 will also be replaced. Patients who do not follow the protocol defined steroid dosing will be considered evaluable and not replaced. Reasons for not following the protocol defined steroid dosing will be reported.

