### **8.2 Follow-Up Procedures**

The following outlines the minimum frequency of follow-up evaluations, it is anticipated that the majority of patients will be evaluated more frequently.

During the first 4 weeks of participation (i.e., through the primary endpoint), patients will be evaluated at least weekly for assessment of their GVHD. Patients will also be evaluated at study

day 42, 56, 90, 180, 1 year and at the time of GVHD flares. Telehealth visits are permitted when in-person visits are not feasible.

Patient compliance with self-administration of prednisone will be assessed by pill diary. Patients will record whether they took their prescribed dose daily for the first 28 days of treatment. Pill diaries will be reviewed at specified study visits and discrepancies with prescribed and actual administration resolved.

PRO tests will be administered at baseline, day 28, day 90 and day 180 visits. Participants will complete the study assessments in-person during their follow-up visits. We will use email, paper copies by US mail, or verbal completion by video or telephone visits when in-person assessment is not feasible. In some cases the baseline PRO will be administered prior to confirming eligibility. If this is the case and patient is a screen fail, the PRO survey will be destroyed. PRO tests are provided in Appendix B.

Infections, as defined in sections 9.1.11 will be closely monitored on this study. In our preliminary data, all patients who developed at least one serious infection did so within 90 days. Given these data, we will monitor for serious infections from start of study treatment through study day 90.

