**TABLE 2: TIME AND EVENTS TABLE**

	Screening	Study day 0	Study day 7	Study day 14	Study day 21	Study day 28 	Study day 42	Study day 56	Study day 90	Study day 180	Study day 365	GVHD Flare 
Windows	Newly diagnosed acute GVHD in need of systemic treatment +/- 1 day	Start of prednisone (or equivalent) therapy	+/- 2 days	+/- 2 days	+/- 2 days	+/- 2 day	+/- 3 days	+/- 3 days	+/- 7 days	+/- 14 days	+/- 21 days	+/- 3 days
Eligibility Review	X											
Concomitant Medication Review 	X	X	X	X	X	X	X	X	X			
Steroid Dose Collection	X	Steroid dose will be collected at each study visit during the first 90 days of study and changes occurring outside of the defined timepoints will be captured on an ad hoc form through study day 90										
Adverse Event Evaluations 	X	Adverse events will be reported from study day 0 through day 56. Report serious adverse events as they occur.										
Infections		Infections as defined in sections 9.1.11 will be reported from study day 0 through study day 90										
Serum Chemistry	X											
GVHD Staging 	X	X	X	X	X	X	X	X	X			X
Height and Weight	X					X		X	X	X	X	
Survival, Relapse & Chronic GVHD Status										X	X	
Patient Reported Outcomes		X 				X 			X 	X 		

(PRO) Assessment 												
	CORRELATIVE STUDIES											
5 ml serum 	X		X	X	X	X						X

 The primary endpoint is assessed on day 28 ±2 days

 Concomitant medication review will report **only** immunosuppressants and other drugs administered during the reporting period for GVHD prevention and treatment.

 Serious adverse events are reported as they occur. Other adverse events can be batch reported after day 56 of study.

 GVHD staging will follow the detailed guidelines provided in the MAGIC Acute GVHD Staging Guidance. GVHD staging and treatment should be reported weekly through day 100 post-HCT for patients co-enrolled on the MAGIC natural history study as per the natural history study calendar of events. Steroid dose changes occurring outside of the defined timepoints will be captured on an ad hoc form through study day 90.

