#### 9.1.11 Serious Infections

Serious infections are defined using the standardized criteria widely used for clinical trials at academic BMT centers, such as life-threatening fungal infections or hemorrhagic cystitis from BK viral infection and include clinically significant CMV infections that require anti-viral treatment regardless of end-organ damage, given the toxicity of such treatments. Serious infections include any viral, bacterial, fungal or parasitic infections that requires systemic treatment.

All grade 2 or 3 infections as defined by the Blood and Marrow Transplant Clinical Trials Network must be reported through day 90.

9.1.12 **Linear growth velocity:** The change in linear growth (height) from baseline to last contact, corrected for age and duration of observation.

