### **14.3 Data Analysis Plans**

The primary endpoint is the proportion of patients who (1) achieve CR, VGPR, or PR by day 28 of treatment without additional immunosuppressive therapy and (2) whose cumulative prednisone exposure is  $\leq 13.5$  mg/kg. The proportion of patients who are successfully treated with  $\leq 13.5$  mg/kg cumulative prednisone dose will be compared to the historical control rate of 14% using a Chi-squared test.

All study patients will be analyzed and when appropriate, subset analyses by ultra-low risk and other patients will be performed. We expect 33 ultra-low risk patients and 17 other patients out of our sample size of 50 study patients, which will be sufficient for subset analyses.

Secondary outcomes such as the overall response rate, duration of response, cumulative incidence of steroid-refractory GVHD, incidence of serious infections (viral, bacterial, fungal, and parasite), cumulative steroid exposure at day 28 and day 90, overall survival at 6 and 12 months, cumulative incidence of NRM at 6 and 12 months, relapse rate at 6 and 12 months, and cumulative incidence of chronic GVHD requiring systemic steroid treatment by one year will be estimated and compared to historical controls.

Continuous variables will be summarized using standard summary statistics such as number of observations (n), mean, standard deviation (SD), minimum and maximum values, median, and 1st and 3rd quartiles. Categorical variables will be summarized in frequency tables as counts and percentages.

Cumulative incidence of non-relapse mortality will be estimated by Gray's method and relapse will be considered as a competing risk. Disease free and overall survival, defined as the time from the transplantation to death or to last follow-up if alive, will be estimated by the method of Kaplan-Meier and the probability curves and 95% confidence intervals will be provided based on the method of Brookmeyer and Crowley.

The exploratory endpoints of linear growth velocity and patient reported outcomes as per Appendix B will be described for patients whose cumulative steroid exposure is  $\leq 13.5$  mg/kg and  $> 13.5$  mg/kg. Linear growth velocity will be expressed as a standard deviation score of the sex- and age-specific mean.

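### Growth velocity runs from baseline to last contact with no minimum interval, so a child who leaves early contributes an SD score that is mostly measurement error

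*Combined protocol and SAP*

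**What the plan says.** Four places in the combined protocol and SAP describe this endpoint, and they do not fix one time span.

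- Synopsis, exploratory objectives: "To calculate growth velocity in study patients over one year".
- Section 4.7: an exploratory endpoint, the change in height relative to sex- and age-specific means, with no horizon.
- Section 9.1.12: "The change in linear growth (height) from baseline to last contact, corrected for age and duration of observation".
- Section 14.3: "Linear growth velocity will be expressed as a standard deviation score of the sex- and age-specific mean". The result is described separately for cumulative steroid exposure up to 13.5 mg/kg and above it. No test is stated and no growth reference is named.

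Table 2 schedules "Height and Weight" at screening and at days 28, 56, 90, 180 and 365. Section 7.7 plans a year of follow-up: "Patients will be followed until 1 year post-enrollment, withdrawal of consent or until death, whichever occurs first". Section 7.9 adds: "Patients who withdraw consent or are lost to follow-up prior to day 28 will also be replaced". Deaths are not mentioned there. Section 8.2 allows remote visits: "Telehealth visits are permitted when in-person visits are not feasible". Section 5.1 admits patients aged 0 to 21 years. The missing-data text in section 14.3 concerns the patient-reported outcomes, not height.

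**The concern.** Last contact is not a fixed time. For a child who dies, withdraws or is lost, it may be day 28, 56 or 90, and each of these is a scheduled height visit. The definition then yields a velocity from one to three months of growth, which is pooled with one-year velocities as if equally informative. The correction for duration rescales the height change, but it also rescales the measurement error.

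Two further gaps follow from the same wording. A last contact may be remote and have no height, and no rule says which height and date to use. Entry up to age 21 also admits patients who may have finished growing, for whom an SD score of velocity may not be meaningful.

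Section 3.3 names inhibition of linear growth as a steroid harm to which children are particularly susceptible. At stake is whether the description of growth by exposure group can be read as intended. The primary test, the sample size and the stopping rule are not affected.

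**Working it through.** The plan states no figure for growth velocity, so there is none to reproduce.

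**Inputs from the documents.** Height visits at days 28, 56, 90, 180 and 365 (Table 2); 50 patients (section 14.2); 17 patients expected outside the ultra-low risk group (section 14.3).

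**Assumptions, not in the documents.** Error SD of one height, e: 0.3 cm (range 0.2-0.5). Reference velocity SD, s: 1.0 cm/yr (range 0.8-1.5). True between-child variance of the SD score: 1. All other children measured at day 365.

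**Step 1: error of one SD score.** For heights d days apart, error SD = √2 × e × (365/d) / s. At day 28 with central values: 1.414 × 0.3 × 13.04 / 1.0 = 5.53.

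| Last height | Central | Range |
|---|---|---|
| Day 28 | 5.53 | 2.46-11.52 |
| Day 56 | 2.77 | 1.23-5.76 |
| Day 90 | 1.72 | 0.76-3.58 |
| Day 180 | 0.86 | 0.38-1.79 |
| Day 365 | 0.42 | 0.19-0.88 |

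The ratio of day 28 to day 365 is 365/28 = 13, whatever e and s are.

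**Step 2: share of total variance, 50 children.** A day-28 child has variance 1 + 5.53² = 31.6. A day-365 child has 1 + 0.42² = 1.18.

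- One child at day 28: 31.6 / (31.6 + 49 × 1.18) = 31.6 / 89.4 = 35% (range 12-61%). The standard error of the mean rises from 0.154 to 0.189.
- Two at day 28: 53% (22-76%).
- Three at day 56: 32% (13-55%).
- Three at day 90: 18% (9-33%). The standard error rises from 0.154 to 0.164.
- Five at day 180: 14% (11-21%).

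**Step 3: one exposure group.** Section 14.3 describes growth by exposure group, so the denominator is smaller. Take 17 as an illustrative size.

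- One child at day 28: 31.6 / (31.6 + 16 × 1.18) = 31.6 / 50.5 = 63%. The variance of the mean is multiplied by 50.5 / (17 × 1.18) = 2.5.
- Over the assumptions, the share runs from 7.04 / (7.04 + 16 × 1.036) = 30% (e = 0.2, s = 1.5) to 133.8 / (133.8 + 16 × 1.781) = 82% (e = 0.5, s = 0.8).
- In a group of 29: 31.6 / (31.6 + 28 × 1.18) = 49%.

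**Step 4: last contact without a height.** If there is no height, the value as defined is missing. If an analyst instead divides an earlier height change by the time to last contact, velocity shrinks by the ratio of the times: 180/365 = 0.49, or 90/365 = 0.25.

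**The case against.** The strongest reply is that very early exits should be uncommon. Patients who stop treatment remain in follow-up (sections 7.6 and 7.8), withdrawals and losses before day 28 are replaced, and non-relapse mortality in Ann Arbor 1 children is given as 2% (section 3.4), about 1 in 50. A day-28 interval requires a child to have the day-28 height and then no later one. Section 14.3 also plans medians and quartiles, which one or two extreme values hardly move. Height error is centred on zero, so it adds noise without a direction.

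Most of this stands, and it limits the size of the problem. A reader might infer that early-exit children dominate the growth result. The documents do not support that, because they give no dropout rate after day 28 and the effect depends on when children leave. Take 2 of 40 children with short intervals, the rest at day 365 and s = 1.0. Compared with leaving the two out, the variance of the mean is 1.06 to 1.19 times as large if they end at day 90, and 2.17 to 3.62 times if they end at day 28 (e = 0.3 and 0.5 cm).

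A reader might also infer that a remote last contact understates velocity by about half. That requires dividing a day-180 height change by 365 days. The duration of observation in section 9.1.12 can equally mean the time between the two heights, and then the value is only missing.

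What does not fall away: replacement covers neither deaths nor exits after day 28; the 2% figure excludes relapse deaths, withdrawals and losses; means, SDs, minima and maxima are planned beside the medians; and the one-year wording still conflicts with last contact.

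**Conclusion.** The definition needs tightening. As written, it pools velocities whose error SD differs up to 13-fold, and the correction for duration does not remove that difference. With the central assumptions, a single day-28 exit would supply about 35% of the variance among 50 children and about 63% in an illustrative group of 17, while exits at day 90 matter little. Early exits can therefore distort the mean-based summaries, but need not.

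The sizes rest on assumed height error and reference SD. The 13-fold ratio does not. How many patients have finished growing is unknown, and without a named reference the age point cannot be quantified. Because the endpoint is exploratory, only described, and not among the outcomes that section 14.2 lists for the phase III decision, this is a cheap improvement of low priority.

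**What to change.** Rewrite section 9.1.12, and align section 14.3 and the synopsis with it:

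- Velocity = (last measured height − baseline height) / (time between those two measurements). Use the day-365 height, otherwise the day-180 height.
- Compute it only when the heights are at least about six months apart. Table 2 allows ±14 days at day 180, so word the limit to admit a visit at 180 − 14 = 166 days.
- Name the growth reference, and calculate the SD score only in the age range where that reference supports a velocity SD.
- List the heights of all other children without a velocity.

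Table 2 already schedules the heights, so the cost is wording. The downside is that a few children will not be evaluable for this endpoint; their number should be reported by exposure group. The six-month limit is a judgement: at day 180 the error SD of the score is about 0.86 under the central assumptions, twice that at day 365, and it should be fixed before the growth data are examined.

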## 9.2 Safety/Toxicity Definitions

### 9.2.1 Safety/Tolerability

The study will use the CTCAE version 5.0 for reporting of adverse events ([https://ctep.cancer.gov/protocoldevelopment/electronic\\_applications/docs/CTCAE\\_v5\\_Quick\\_Reference\\_8.5x11.pdf](https://ctep.cancer.gov/protocoldevelopment/electronic_applications/docs/CTCAE_v5_Quick_Reference_8.5x11.pdf)).

## 10.0 ADVERSE EVENTS

### 10.1 Adverse Event Reporting Requirements

Adverse event (AE) monitoring and reporting is a routine part of every clinical trial and is done to ensure the safety of subjects enrolled in the studies as well as those who will enroll in future studies using similar strategies. Data on adverse events will be collected from the time of the initiation of study treatment until day 56 as defined in section 10.2. Any serious adverse event that occurs after day 56 that is considered related to the study treatment must also be reported. Serious Adverse Events (SAEs) will continue to be followed until:

- Resolution or the symptoms or signs that constitute the serious adverse event return to baseline;
- There is satisfactory explanation other than the study treatment for the changes observed; or
- Death.

The investigator is responsible for the detection, documentation, grading and assignment of attribution of events meeting the criteria and definition of an AE or SAE. The definitions of AEs and SAEs are given below. It is the responsibility of the principal investigator to ensure that all staff involved in the trial is familiar with the content of this section.

Any medical condition or laboratory abnormality with an onset date before initial study treatment is considered to be pre-existing in nature. Any known pre-existing conditions that are ongoing at time of study entry should be considered medical history.

All events meeting the criteria and definition of an AE (CTCAE grade 3 or higher) or SAE, as defined in Section 10.2.2, occurring from the initial study treatment administration through study

day 56 days must be reported as an adverse event in the patient's source documents and on the CRF.

## **10.2 Definitions**

### **10.2.1 Adverse Event**

An adverse event (AE) is any untoward medical occurrence in a patient receiving study treatment and which does not necessarily have a causal relationship with this treatment. An AE can be any unfavorable and unintended sign (including an abnormal laboratory finding), symptom, or disease temporally associated with the use of an experimental intervention, whether or not related to the intervention.

- Diagnostic and therapeutic non-invasive and invasive (i.e., surgical) procedures will not be reported as adverse events. However, the medical condition for which the procedure was performed must be reported if it meets the definition of an adverse event unless it is a pre-existing (prior to protocol treatment) condition.
- Event reporting for GVHD treatment protocols can be complicated and confusing for investigators, data managers, and regulatory oversight bodies because patients typically develop numerous complications as part of the typical treatment course not related to study therapy. Furthermore, transplant-related complications often occur both simultaneously and in series, as one complication leads to a series of downstream events. Therefore, a well-conceived event reporting plan separates background transplant and GVHD noise as might be seen with any transplant where GVHD develops from study related events that are relevant to patient safety. On this study, we will not report any CTCAE grade 1 and 2 adverse events (which make up the majority of events) unless the investigator determines the event should be reported to protect subject safety. Furthermore, because vast experience with corticosteroid treatment for GVHD in children already exists, and this is a de-escalation study, with the exception of infections (which are also a study endpoint), adverse events deemed not related or unlikely related to tapering steroids (e.g., symptomatic hypoglycemia or steroid withdrawal symptoms) are also not required to be reported. Changes in GVHD staging, treatment response, will be reported as study endpoints and are not considered adverse events on this trial with the exception of the development of steroid refractory GVHD.
- After study day 56, adverse events should only be reported if they are unexpected or fatal regardless of attribution. All serious adverse events. Reporting of such events should include the investigator's assessment as to whether the event should be attributed to any of the HCT procedure itself, GVHD, or its treatment. An event may be attributable to all, some, or one of these categories.
- Abnormal laboratory values or test results constitute adverse events only if they induce clinical signs or symptoms or require therapy and otherwise meet the criteria for a reportable adverse event as defined above. They are to be captured under the signs, symptoms or diagnoses associated with them.

- All serious adverse event reporting will cease if patient has relapse or second transplant.

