The doctors conducting this research have developed a blood test (GVHD biomarkers) that predicts whether a patient will respond well to steroids. In a study of 85 pediatric patients (age up to 21 years), they found that children who have low GVHD biomarkers at the start of treatment and for the first two weeks of treatment have a very high response rate to steroids (96%) that lasts. In this study, we will monitor GVHD symptoms and biomarkers during treatment and decrease the steroid treatment by 50% in patients who have GVHD that is expected to respond very well to treatment. We will do this by starting treatment at a lower dose and tapering quickly so long as the biomarkers remain low and the symptoms are responding. To avoid undertreating patients who may need higher doses, we will increase the steroid dose if symptoms worsen or biomarkers increase. We will assess how many patients respond well to lower steroid dosing and what steroid complications develop. We will also use surveys to obtain patient's own assessment of their quality of life (down to age 5 years). We hope that the results of this research will help us develop treatments for GVHD that are both effective and safer than currently available.

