### **7.2 Toxicities and Dosing Delays/Dose Modifications**

Steroid treatment is the standard of care for acute GVHD. The goal of this study is to reduce the toxicities of steroid treatment. Toxicities of steroid treatment that are not captured as study endpoints will be assessed according to the NCI Common Terminology Criteria for Adverse Events (CTCAE), version 5.0 and reported according to the Time and Events Table (Section 6.2).

It is anticipated that prednisone doses not in accordance with **Table 1** may occur. For example, a patient with life-threatening steroid toxicities may require discontinuation of treatment. Prednisone dosing delays and dose modifications that deviate from the prescribed prednisone taper will be monitored and their reasons reported.

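### Section 10.2.1 ties the adverse-event exemption to steroid tapering, so reporting of non-serious, non-infectious grade 3 or higher toxicities of steroid exposure becomes optional, contrary to 10.1, 7.2 and Table 2

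*Combined protocol and SAP*

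**What the plan says.** Four places in the combined protocol and SAP set the scope of adverse-event reporting.

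- **Section 10.2.1** first removes low grades: "we will not report any CTCAE grade 1 and 2 adverse events", unless the investigator thinks a report is needed for subject safety. It then adds an attribution filter: reports are not required for "adverse events deemed not related or unlikely related to tapering steroids", with hypoglycaemia and steroid withdrawal given as examples in parentheses. The reason given is "because vast experience with corticosteroid treatment for GVHD in children already exists, and this is a de-escalation study", and one class is kept in: "with the exception of infections (which are also a study endpoint").
- **Section 10.1** sets the general duty. "All events meeting the criteria and definition of an AE (CTCAE grade 3 or higher) or SAE", from first study treatment through day 56, has to go into the source documents and onto the CRF. That sentence contains no attribution filter.
- **Section 7.2** states that the goal of the study is to reduce steroid toxicity, and commits as follows: "Toxicities of steroid treatment that are not captured as study endpoints will be assessed" by CTCAE version 5.0 and reported according to the Time and Events Table.
- **Table 2 (Time and Events Table)** has an adverse-event row running from day 0 to day 56, also with no attribution filter.

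The lay summary (2.0) tells families: "We will assess how many patients respond well to lower steroid dosing and what steroid complications develop".

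**The concern.** The filter asks whether an event is related to tapering. Many recognised steroid toxicities are effects of exposure. Hyperglycaemia and hypertension appear in the toxicity table in 11.1 as prompt effects, within two to three weeks, so they would arise inside the day 56 window. Neither is caused by lowering the dose. A site applying 10.2.1 literally may leave a non-serious grade 3 case unreported, while a site applying 10.1 or 7.2 must report the same case.

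The synopsis lists eleven centres. If they resolve the conflict differently, counts of these toxicities will partly reflect which section each centre followed. That matters in a trial whose stated purpose is less steroid toxicity, and whose lay summary names high blood sugar and high blood pressure as complications of steroid treatment.

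**Working it through.** No arithmetic applies. The check sets the sections side by side, by type of event, through day 56.

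1. **Infections.** Kept in by the exception inside the 10.2.1 sentence, and collected separately to day 90 under 9.1.11 and Table 2. No conflict.
2. **Serious adverse events caused by steroid exposure.** The SAE table in 10.4 requires all SAEs to day 56 for every attribution category, including unrelated. The 10.2.1 filter has no explicit carve-out for SAEs, but 10.1 and 10.4 are clear. These stay reportable.
3. **Grade 1 and 2 toxicities.** Excluded by the separate grade rule in 10.2.1 and by the grade 3 threshold in 10.1. The tapering filter makes no difference to them.
4. **Non-serious, non-infectious grade 3 or higher toxicities of steroid exposure.** Required by the closing sentence of 10.1, and required by 7.2 with Table 2 where they are not endpoints. Not required by 10.2.1. This is a direct conflict.

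Two further checks bear on item 4.

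- **Which reading of the filter does the text favour?** The parenthetical examples, hypoglycaemia and steroid withdrawal, are effects of reducing the dose, so relatedness here appears to mean relatedness to dose reduction. The parenthesis could even be read as listing the exempt events. By contrast, the attribution scale in 10.3.2 runs against study treatment. An event rated definitely related on that scale could still be exempt under 10.2.1.
- **Do other data fill the gap?** No endpoint in 4.5 to 4.7 measures hyperglycaemia or hypertension. Patient-reported outcomes cover mobility, anxiety, depression, fatigue and sleep, and so touch mood and muscle weakness, but the surveys begin at age 5 by proxy (13.3) while eligibility begins at age 0 (5.1.5).

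**The case against.** The strongest defence has four parts.

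**The sections can be read together.** Section 10.1 says adverse-event data are collected as defined in 10.2, so 10.2.1 could be taken as narrowing it. A site that reports every grade 3 or higher event also satisfies all the sections, because 10.2.1 only waives a duty. Both points soften the conflict without removing it. The closing sentence of 10.1 is mandatory and unqualified, 7.2 and Table 2 do not rely on the cross-reference, and a site that uses the waiver falls short of them.

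**Tapering may simply mean the study intervention.** Section 14.1 describes the intervention as a structured steroid taper. That reading is possible, but the examples in 10.2.1 point the other way, and a site cannot settle it from the text.

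**The filter has a sound purpose.** Section 10.2.1 explains that background transplant complications would swamp the study-related events. That stands, and it is a reason to correct the filter rather than delete it.

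**Harm from steroids is measured elsewhere.** A reader might infer that the filter removes the trial's data on steroid harm, or that only infections are protected. The documents do not support either. All SAEs to day 56 are reported whatever the attribution. Section 3.3 treats serious infections as a surrogate for overall steroid morbidity. Patient-reported outcomes, growth and cumulative steroid dose are collected separately. Waiving a report also does not forbid it. This part of the defence stands, and it confines the point to item 4 of the check.

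**Conclusion.** The conflict between 10.2.1 on one side and 10.1, 7.2 and Table 2 on the other is real and should be corrected. Its reach is limited to non-serious, non-infectious grade 3 or higher toxicities of steroid exposure through day 56, for which capture may be incomplete and uneven across sites. This rests on the narrow reading of tapering, which the examples in 10.2.1 favour but do not compel.

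Two stronger conclusions should not be drawn.

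- A reader might size the loss from the 11.1 toxicity table, which puts hyperglycaemia at 5 to 20 per 100 children: 0.05 × 50 = 2.5 to 0.20 × 50 = 10 patients. Those frequencies are not restricted to grade 3 or higher, and grades 1 and 2 are excluded by a different rule. The share that is grade 3 or higher and non-serious is not given, so this is not an estimate of what the filter loses. Hypertension is listed at under 5 per 100.
- A reader might infer that the filter is what stops the trial from showing a fall in toxicity. The trial has one arm, 14.3 does not list non-infectious adverse events among the outcomes compared with historical controls, and the documents give no historical rate for them. Complete reporting would describe these toxicities but would not show a reduction.

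**What to change.** 1. In 10.2.1, for grade 3 or higher events through day 56, replace relatedness to tapering with relatedness to *steroid treatment or its tapering*. Place the parenthetical examples so that it is clear whether they illustrate reportable or exempt events.
2. In the closing sentence of 10.1, state that the duty for non-serious adverse events is subject to the 10.2.1 filter. Leave the duty for SAEs as it is, in line with 10.4.
3. Check 7.2 and the adverse-event row of Table 2 against the amended wording so that all four places agree. Section 7.2 cites Section 6.2 for the Time and Events Table, which sits under 8.2; correct this at the same time.
4. Report grade 3 or higher steroid toxicities descriptively, as numbers and percentages of patients. A breakdown by day 28 cumulative dose is not recommended as evidence of benefit: section 7.1 recommends higher doses for patients who do not respond, so exposure is confounded with response.

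The cost is an amendment to a few clauses and some additional grade 3 or higher forms through day 56. Unrelated transplant events stay filtered. Deleting the exemption altogether would also resolve the conflict, but it would bring those unrelated events back, which is a trade-off for the sponsor rather than a necessary correction.
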